3.2 Secondary Objectives

Objective: To evaluate efficacy as measured by the overall response rate and rate of 6 month PFS in subjects with persistent/recurrent, loco-regional or metastatic SCCA of the anorectal as determined by irRECIST

Objective: To evaluate the safety and tolerability of ADXS11-001 in subjects with persistent/recurrent, loco-regional or metastatic SCCA of the anorectal canal by NCI CTCAE 4.0.

Objective: To evaluate the additional parameters of efficacy (duration of response, PFS and overall survival) of ADXS11-001 in subjects with persistent/recurrent, loco-regional or metastatic SCCA of the anorectal canal as determined by RECIST 1.1 and irRECIST.

4 BACKGROUND & RATIONALE

4.1 Background

4.1.1 ADXS11-001 Immunotherapy

ADXS11-001 is a live attenuated *Listeria monocytogenes* (*Lm*)-LLO immunotherapy, developed for the treatment of human papilloma virus (HPV)-associated cancers. ADXS11-001 is bioengineered to secrete an antigen-adjuvant fusion protein (tLLO-HPV-E7) consisting of a truncated fragment of the listeriolysin O (tLLO) fused to the full length E7 peptide of HPV-16.

ADXS11-001 is phagocytized by antigen-presenting cells (APCs) and secretes Listeriolysin O (LLO)-tumor antigen fusion proteins within the cytoplasm of the APC thereby allowing the generation of a new population of tumor antigen specific cytotoxic T lymphocytes (CTLs) driven by the adjuvant properties of LLO. These tumor-specific CTLs can then take advantage of the acute immunologic response to the live vector to facilitate infiltration into the tumor, enabling them to access and destroy tumor cells.

The advantages that *Lm* possesses as a vector are rooted in its biology. It is a beta hemolytic Gram positive facultative intracellular bacterium that has been used to study cell mediated immunity for decades.[1] *Lm* are preferentially taken up by APCs and, unlike other intracellular bacteria like Salmonella, *Lm* escapes into the cytoplasm of the host cell by disrupting the phagosomal membrane. Also unlike Salmonella, *Lm* is a Gram positive organism, thus, does not release endotoxin, a rate limiting attribute of Salmonella. Because *Lm* quickly leaves the circulation becoming an intracellular infection and because it replicates in the cytoplasm, humoral immunity does not play a major role in combating listerial infections.

Lm has other useful properties, such as stimulating monopoiesis, stimulating the differentiation and maturation of APCs, and the generation of a particularly strong innate and adaptive cellular immune response.[1, 2] The ability to deliver antigen to the cytosolic compartment of APCs in order to develop human leukocyte antigen Class I

presentation to induce CD8+ cytotoxic T-cell responses appears to be an important aspect of developing an effective therapeutic antitumor therapy. Peptides derived from *Lm* in the phagolysosome and the cytosol can be presented by both the major histocompatibility complex (MHC) Class I and Class II molecules, inducing both CD4+ and CD8+ T cell responses. There is evidence that *Lm* also gets into tumors, probably carried by infected macrophages and neutrophils. One potential consequence of this is the observed ability of live *Lm* vector that secrete an LLO-antigen fusion, but not those that secrete only an antigen, to diminish regulatory T-cells (Tregs) within the tumor, but not in the spleen or normal peripheral tissues.

As a drug product, ADXS11-001 is administered as an IV infusion given every 3-4 weeks. It has no direct effect on tumor tissue, but is designed to stimulate the subject's own immune system to generate an effective immune response targeting a tumor-associated antigen like HPV-E7. Clinical benefit can manifest as a slowing of tumor growth, a stabilization of tumors, or a partial or complete response of the tumors.[3] Collectively, the spectrum of clinical benefits is captured as relative delays in tumor progression and/or apparent prolonged survival.

4.1.2 Preclinical and Clinical Trial Data

Refer to the Investigator's Brochure for detailed preclinical and clinical data.

4.2 Rationale for Trial and Selected Subject Population

Human papilloma viruses are spread by direct human contact. Infection of squamous mucosal epithelial cells by high risk strains of HPV can result in the transformation of squamous epithelial to a pre-malignant phenotype that can progress to malignancy. High risk HPV strain E6 and E7 gene products interfere with the expression and function of the host tumor suppressor gene products of P53 and Rb in the host cell. This process can occur in the uterine cervix and can lead to cervical cancer, the oropharyngeal mucosa of the tonsils or base of the tongue, and lead to squamous cell carcinoma of the oropharynx, or the mucosal epithelium of the anus leading to anorectal cancer.

While it is estimated that 80% of sexually active individuals are exposed to oncogenic strains of HPV, the percentage that develop dysplastic or malignant lesions is considerably less.[4] This is presumably because many individuals can clear the viral infection immunologically. However, in some individuals, the virus is not cleared and expressions of viral gene products can lead to malignancy over time.

Various mechanisms have been proposed for the resistance of human solid tumors to immune recognition and obliteration, including the recruitment of regulatory T cells (Tregs), myeloid-derived suppressor cells (MDSC), and local secretion of inhibitory cytokines that mediate immune tolerance in tissue or tumor microenvironments. The occurrence of HPV-induced cancer is strongly associated with failure to mount a strong HPV-specific type 1 T-helper and cytotoxic T-lymphocyte response.[5-7]

[figure not shown]
However, the inhibitory action of HPV-specific Tregs within the tumor microenvironment is not the only mediator of immune tolerance contributing to the immunologic resistance of HPV-associated malignancy. Recent evidence also suggests that tumors can co-opt physiologic mechanisms of tissue protection from inflammatory destruction via up-regulation of immune inhibitory ligands.

[figure not shown]
The mechanism of oncogenesis from high-risk HPV infection in squamous mucosal epithelium is consistent, whether the site of infection is the cervix or the oral or anal mucosa. Persistence of the virus and its inhibition of tumor suppressor functions can lead to the development of dysplasia or malignant carcinoma. Anorectal cancer, although relative rare has been steadily increasing over the last 50 years. And while both survival and locoregional control is good for patients with early stage anorectal cancer, for those patients with high risk and/or recurrent metastatic disease the unmet medical need remains high.[8, 9] The epidemiology of anorectal cancer demonstrates that high-risk HPV has been reported in approximately 90% in patients with squamous cell cancer of the anorectal canal, with serotypes HPV 16 and 18 being the most common.[10] Given the activity that ADXS11-001 has demonstrated in metastatic squamous cell cancer of the cervix,[3] which are histologically and epidemiologically similar to anorectal cancer, evaluation of ADXS11-001 in patients with anorectal cancer seem logical.

[figure not shown]
Currently there is an ongoing clinical study in subjects with high-risk locally advanced squamous anal cancer which evaluates ADXS11-001 therapy prior to, and following standard of care radiotherapy and concurrent 5FU/mitomycin C (MMC) (NCT #01671488). To date 10 subjects have been enrolled. Preliminary safety data from this ongoing study are consistent with those observed with ADXS11-001 treatment to date. The current study seeks to evaluate ADXS11-001 in the metastatic population. The standard of care for patients with metastatic disease was established several years ago with a combination regimen of 5FU and cisplatin. Response rates with this combination range between 40-50% with median overall survival of 34.5 months.[11, 12] While efficacious, patients will recur and eventually succumb to their disease. The need to evaluate new therapies, particularly those targeted at HPV, such as ADXS11-001 is warranted.

4.2.1 Rationale for Dose Selection/Regimen/Modification

4.2.1.1 Summary of Safety of ADXS11-001

[figure not shown]

4.2.2 Delayed/Late *Listeria* Infection

In a Phase 1 clinical study, in the absence of antibiotics, *Lm* was rapidly cleared from the blood. No *Lm* was detected in the blood, urine or feces of any subject beyond 48 hours post-dosing and at the highest dose of ADXS11-001 tested (1×10^{10} CFU).[13]

wt-Lm is known to form and persist within biofilms especially on medical devices despite antibiotic treatment.[14] Although rare, medical device-related infections such as ventriculo-peritoneal shunt infection, peritoneovenous shunt infection, and prosthetic joint infection have been reported.[15-18] ADXS11-001 is highly sensitive to antibiotics such as ampicillin and trimethoprim/sulfamethoxazole which can be an effective treatment regimen for listeria infection. Therefore, subjects with implanted medical device(s) that pose a high risk for colonization and/or cannot be easily removed are excluded from this study. In addition, all subjects will receive a course of oral antibiotics beginning on Day 4 (approximately 72 hours) after each dose of ADXS11-001 and for 6 months following the last dose of ADXS11-001 to aid in the eradication of the bacteria.

[figure not shown]
[figure not shown]
4.2.2.1 ADXS11-001 – Rationale for Dose Selection and Regimen

ADXS11-001 is a live attenuated strain of *Listeria monocytogenes* (*Lm*) that has been

The AEs associated with this class of agents seem to be directly related to innate immune effects associated with the infusion of the live attenuated bacteria. These typically consist of Grade 1 and 2 cytokine release symptoms (e.g., fever, chills, rigors, headache, nausea, vomiting, tachycardia, shortness of breath, hypotension, and rash) which typically occur 2-4 hours after ADXS11-001 infusion and usually resolve within 12-24 hours. The symptoms appear to be related to the number of CFU infused over time. Pretreatment with hydration, oral nonsteroidal anti-inflammatory drugs (NSAIDs), antihistamines, histamine H2-receptor antagonists and antiemetics may reduce the incidence of these symptoms.

With ADXS11-001, live bacteria has not been recovered from subjects after 48 hours following completion of the infusion. A 7-day course of oral antibiotics is given beginning on Day 4 post dose to help ensure clearance of the vector. There is no specific target blood level that needs to be achieved in order for ADXS11-001 to compete with a target or bind to a receptor. Therefore, maximum concentration (C_{max}), minimum concentration (C_{min}), and half-life of ADXS11-001 are not relevant based on pharmacology.

The complex mechanism of action of ADXS11-001 includes elements that may be dose related. For example, the generation of T-cells may require a minimum effective dose in order for the body to respond. In previously completed, as well as ongoing clinical studies, a dose of 1×10^9 CFU has demonstrated clinical responses and appears to meet this minimum requirement. Additionally, in patients with advanced disease there may be an added benefit to treating with higher doses and repeating treatments until progression or complete response

Patients with metastatic or recurrent anorectal cancer have advanced disease, extremely limited treatment options and a poor long-term prognosis. Therefore, these patients should receive the most aggressive treatment that can be administered safely to optimize their opportunity for clinical benefit. Since the results from the ongoing Phase 1 study have shown that a dose of 1×10^{10} CFU can be safely administered and is well-tolerated by patients with an advanced HPV-related disease (cervical cancer), a dose of 5×10^9 CFU of ADXS11-001 has been selected for use in this clinical study. This dose has also been shown that it can be safely administered and was well-tolerated in a clinical study of patients with advanced HPV disease. It is also a dose level below the dose (1×10^{10} CFU) which has been established as the RP2D in a clinical study in an advanced disease HPV population. Finally, this dose was selected to offer patients with advanced anal cancer the greatest opportunity to receive clinical benefit during their participation in the study. The safety and tolerability of this dose will be evaluated in this population on an individual and cumulative subject basis. Defined stopping rules are in place which require safety data to be evaluated and the study 'stopped' if specific individual patient and/or cumulative patient criteria are met. The 5×10^9 dose will be evaluated when the study is 'stopped' based on meeting the protocol-defined criteria in order to determine if it is safe to proceed at this dose level or a lower dose should be considered. All subjects will

receive treatment for up to two years, until confirmed disease progression or until a complete clinical response is achieved.

4.2.3 Rationale for Endpoints

4.2.3.1 Efficacy Endpoints

The evaluation of efficacy for both the parts of the study will utilize CT or magnetic resonance imaging (MRI) to assess tumor response as well as PFS measured by RECIST 1.1 and irRECIST. These endpoints are well established and commonly used to evaluate signs of clinical activity and efficacy.

4.2.3.2 Safety Endpoints

The safety objective of this trial is to characterize the safety and tolerability of ADXS11-001 in subjects with metastatic SCCA of the anorectal canal. The safety analysis will be based on subjects who experience toxicities as defined by NCI CTCAE v 4.0. Safety will be assessed by quantifying the toxicities and grades experienced by subjects who have received ADXS11-001, including SAEs.

The attribution to drug, time-of-onset, duration of the event, its resolution, and any concomitant medications administered will be recorded. AEs will be analyzed including but not limited to all AEs, SAEs, fatal AEs, changes in physical examinations, vital sign measurements and clinical laboratory changes.

4.2.4 Study Stopping Rules

Rules for temporary suspension of study for death due to non-progressive disease, hematologic and non-hematologic events related to ADXS11-001 treatment

The Advaxis medical monitor and Project Manager as well as other key personnel associated with the trial (e.g. CRO Medical Monitor, Primary Investigator), as appropriate, will monitor death due to non-progressive disease and hematologic and non-hematologic toxicities for individual subjects in real-time and trial-level cumulative toxicities on a monthly basis. These events must be deemed by the Investigator at the site to have some degree of “relatedness” to ADVXS11-011 treatment (e.g. definitely, probably or possibly related) in order to be considered for evaluation. The assessment of cumulative trial-level toxicities will not begin until at least 5 subjects have received a dose of ADXS11-001 and evaluated for death and individual toxicity events following the completion of the initial 3-week treatment period. The guidelines below will be used to determine the threshold of cumulative events that will result in temporary suspension of enrollment for new subjects and dosing for any active subject until a thorough of the cumulative information is evaluated and a risk/benefit assessment conducted.

- Death (other than death related to disease progression) that occurs within 30 days of the ADXS11-001 infusion
-

- >30% Grade 3 or greater non-hematologic adverse events that are at least possibly related to ADXS11-001
- >30% Grade 4 or greater hematologic adverse events that are at least possibly related to ADXS11-001

The assessment of an individual subject event which meets the criteria as defined above and has been determined by the investigator to be related to ADXS11-001 treatment will begin as soon as all required and relevant information is received. The same project team personnel will review all of the information and determine an appropriate course of action (e.g., temporarily suspending enrollment and ongoing treatment in active subjects; temporarily suspending enrollment and allowing treatment in active subjects to continue) based on a thorough review pertaining to the event.

The Sponsor will send a written communication to the investigative sites when a decision is made based on all available information from an individual subject or the cumulative data to temporarily suspend future enrollment and/or the continued doing of active subjects. The communication will contain information about the event(s) and the immediate steps which must be taken in order to comply with the Sponsor's decision. The investigative sites will also receive written notification from the Sponsor when the enrollment of new subjects and dosing for active subjects may resume.

5 METHODOLOGY

5.1 Entry Criteria

5.1.1 Inclusion Criteria

This study will include subjects with persistent/recurrent, loco-regional or metastatic SCCA of the anorectal canal.

For subjects to be eligible they:

1. Must have histopathologic diagnosis of squamous cell cancer of the anorectal canal.
 2. Must have received at least one line of therapy for their metastatic disease. However patients deemed by their investigator as not optimal candidates for chemotherapy (e.g., drug allergy, ototoxicity, renal insufficiency) would be considered eligible.
 3. Be willing and able to provide written informed consent for the trial.
 4. Be ≥ 18 years of age on day of signing informed consent.
 5. Have measurable disease based on RECIST 1.1
 6. Have Eastern Cooperative Oncology Group (ECOG) performance status of 0 or 1.
 7. Demonstrate adequate organ function as defined in [Table 3](#).
-

Table 3 Adequate Organ Function Laboratory Values

System	Laboratory Value
Hematological	
Absolute neutrophil count (ANC) ^a	≥1,000 /mcL
Platelets	≥75,000 / mcL
Hemoglobin	≥9 g/dL or ≥5.6 mmol/L
Renal	
Serum creatinine OR Measured or calculated ^b creatinine clearance (GFR can also be used in place of creatinine or CrCl)	≤1.5 X upper limit of normal (ULN) OR ≥50 mL/min for subject with creatinine levels >1.5 X institutional ULN
Hepatic	
Serum total bilirubin	≤1.5 X ULN OR Direct bilirubin ≤ULN for subjects with total bilirubin levels >1.5 ULN
AST (SGOT) and ALT (SGPT)	≤2.5 X ULN OR ≤5.0 X ULN for subjects with liver metastases
Coagulation	
International Normalized Ratio (INR) or Prothrombin Time (PT)	≤1.5 X ULN unless subject is receiving anticoagulant therapy as long as PT or INR is within therapeutic range of intended use of anticoagulants
Activated Partial Thromboplastin Time (aPTT)	≤1.5 X ULN unless subject is receiving anticoagulant therapy as long as aPTT is within therapeutic range of intended use of anticoagulants
^a ANC, Platelets, Hemoglobin requirement cannot be met by the use of recent transfusions, or growth factor support (G-CSF, erythropoietin, etc) within 2 weeks prior to treatment initiation.	
^b Creatinine clearance should be calculated per institutional standard.	

8. Female subjects of childbearing potential must not be breastfeeding and have a negative urine or serum pregnancy test within 72 hours prior to receiving the first dose of study medication. If the urine test is positive or cannot be confirmed as negative, a serum pregnancy test will be required.
9. Female subjects of childbearing potential should be willing to use 2 methods of birth control for the course of the study through 120 days after the last dose of study medication (see [Section 5.7.2](#)).
10. Male subjects should agree to use an adequate method of contraception starting with the first dose of study therapy through 120 days after the last dose of study therapy.
11. Must have a washout period of the following prior to first dose of study treatment:

- a. **14 days** from completing prior standard of care therapy, with the exception of MMC and palliative radiation therapy for disease-related pain.
- b. **6 weeks** from the last dose of MMC, given the delayed bone marrow suppression that can be experienced with MMC.
- c. **28 days** from treatment with investigational device/therapy or 3 times the half-life in the case of monoclonal antibodies, whichever is longer
- d. **7 days** from treatment with systemic steroid therapy or any other form of immunosuppressive therapy
- e. **30 days** from treatment with live vaccine

Note: Examples of live vaccines include, but are not limited to, the following: measles, mumps, rubella, chicken pox, yellow fever, rabies, BCG, typhoid, and intranasal influenza vaccines (e.g., Flu Mist®). Seasonal influenza vaccines for injection are generally killed virus vaccines and are allowed.

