5.6.4 Management and Surveillance of Listeria During Study Participation

A subject who experiences a fever (CTCAE Grade 1 or greater) 24 hours following the completion of ADXS11-001 infusion should be started on NSAIDs, hydration and other appropriate measures to treat the fever. In the event that the fever persists or worsens 48 hours following the completion of ADXS11-001 infusion then oral or broad spectrum IV antibiotics should be considered based on the subject's medical condition. If the fever remains unresponsive to oral/IV antibiotics 72 hours following the completion of the infusion then a blood culture should be obtained to evaluate for listeremia and determine the appropriate treatment course for the subject.

All subjects will receive a 6 month course of an oral antibiotic regimen as a prophylactic measure approximately 72 hours following the completion of the last dose of ADXS11-001 treatment or at the time of study discontinuation. This additional safety measure is intended to eradicate *Lm* from the body.

Lm surveillance monitoring will also be initiated following the completion of the last dose of ADXS11-001 treatment or at the time of study discontinuation. This monitoring will include obtaining a blood sample for CBC, CMP, including CRP and ESR, and blood cultures for the detection of listeria. Testing will be performed on all subjects who have received at least one dose of ADXS11-001 and occur every 4 months (± 2 weeks) for 3 years.

Should a diagnosis of listeriosis occur at any point after treatment with ADXS11-001 is completed immediate, intensive IV antibiotic treatment (e.g. Ampicillin +/- Gentamicin or other IV antibiotic regimen as indicated) is required. An infectious disease consult should be obtained. Based on each individual subject's case and at the discretion of the treating physician, the removal of any foreign medical object that has been present since treatment with ADXS11-001 was initiated may be warranted. It is extremely important that the investigator, his/her research staff, other healthcare providers involved in the care of the subject as well as each subject participating in this study are educated and made aware of the signs and symptoms of listeriosis and the potential for delayed listeremia/listeriosis. Educational materials for the investigator, research staff, health care providers and patients will be prepared and educational training performed.

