5.7.2 Contraception

ADXS11-001 may have adverse effects on a fetus in utero. Furthermore, it is not known if ADXS11-001 has transient adverse effects on the composition of sperm. Prior to enrollment, all male and female study candidates with reproductive potential must be advised of the importance of avoiding pregnancy during trial participation and the potential risk factors for an unintentional pregnancy. Women of childbearing potential is defined as females who have experienced menarche and who have not undergone successful surgical sterilization (hysterectomy, bilateral tubal ligation, or bilateral oophorectomy), are not postmenopausal (defined as amenorrhea ≥ 12 consecutive months or women on hormone replacement therapy with a documented serum follicle stimulating hormone level > 35 mIU/ml). Even women who are using oral, implanted, or injectable contraceptive hormones or mechanical products, such as an intrauterine device or barrier methods (diaphragm, condoms, spermicides), to prevent pregnancy, who are practicing

abstinence, and who have a sterile partner (eg, vasectomy) should be considered of childbearing potential.

All women of childbearing potential must have a negative pregnancy test within 72 hours prior to receiving ADXS11-001. The minimum sensitivity of the pregnancy test must be 25 IU/L or equivalent units of human chorionic gonadotropin. If the pregnancy test is positive, the patient must not receive ADXS11-001 and may not be enrolled in the study.

Male subjects may be enrolled if they are willing to use an adequate method of contraception. Women of childbearing potential may be enrolled if they are willing to use 2 methods of birth control. The 2 birth control methods can be 2 barrier methods or a barrier method plus a hormonal method to prevent pregnancy.

The following are considered adequate barrier methods of contraception: diaphragm, condom (by the partner), copper intrauterine device, sponge, or spermicide. Appropriate hormonal contraceptives will include any registered and marketed contraceptive agent that contains an estrogen and/or a progestational agent (including oral, subcutaneous, intrauterine, or intramuscular agents).

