Subjects should be informed that taking the study medication may involve unknown risks to the fetus (unborn baby) if pregnancy were to occur during the study. In order to participate in the study all males and female study candidates of reproductive potential must adhere to the contraception requirement (described above) from Visit 1 through 120 days post last ADXS11-001 administration. If there is any question that a subject will not reliably comply with the requirements for contraception, that subject should not be entered into the study.

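### Required contraception for women of childbearing potential ends about two months before the post-treatment antibiotic course meant to clear the live vector

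*Combined protocol and SAP*

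**What the plan says.** **Contraception.** Inclusion criterion 9 (Section 5.1.1) asks women of childbearing potential to be willing to use "2 methods of birth control for the course of the study through 120 days after the last dose of study medication" and refers to Section 5.7.2. That section makes the requirement an obligation for men and women, running "from Visit 1 through 120 days post last ADXS11-001 administration". It gives as the reason that "ADXS11-001 may have adverse effects on a fetus in utero". It also says that candidates with reproductive potential "must be advised of the importance of avoiding pregnancy during trial participation".

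**Post-treatment antibiotics.** Section 4.2.2 says that subjects take oral antibiotics after each dose and "for 6 months following the last dose of ADXS11-001 to aid in the eradication of the bacteria". Section 5.6.4 states: "All subjects will receive a 6 month course of an oral antibiotic regimen as a prophylactic measure". It describes the purpose as follows: "This additional safety measure is intended to eradicate" Lm from the body. Section 7.1.6.2 and footnote 8 of the Schedule of Events start the course about 72 hours after the last dose, or at discontinuation.

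**Clearance data.** Section 4.2.2 reports from a Phase 1 study that no Lm "was detected in the blood, urine or feces of any subject beyond 48 hours post-dosing", without antibiotics and at doses up to 1×10^10 CFU.

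**After the course.** Section 5.6.4 adds Lm surveillance every 4 months for 3 years, which the Summary (Section 1) counts as part of the study.

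**The concern.** The protocol applies two precautions to the same hazard, possible persistence of a live vector after dosing, and they stop at different times. The antibiotic course assumes that the vector may need active eradication for six months. The contraception rule stops at 120 days. Between those dates a woman can have met every contraception requirement and conceive while still taking the eradication course.

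The possible harm is serious. Section 5.6.3.1 says that wild-type listeriosis in pregnancy can cause pregnancy loss, preterm birth and life-threatening neonatal infection. ADXS11-001 is attenuated, so this shows the kind of harm and not its frequency.

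Little else in the schedule would pick up a pregnancy in this window. Pregnancy testing stops at End of Therapy, and the surveillance visits include blood counts, chemistry, inflammatory markers and blood cultures, but no pregnancy test.

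**Working it through.** The plan gives no figure for this interval, so there is none to reproduce. The check is a day count from the last ADXS11-001 dose (Day 0).

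**Inputs**
- End of required contraception: Day 120 (Inclusion 9; Section 5.7.2).
- Start of the antibiotic course: Day 0 if counted from the last dose (Section 4.2.2); Day 3 with the 72-hour start (Sections 5.6.4 and 7.1.6.2; Schedule of Events footnote 8).
- Length of the course: 6 months. The protocol does not convert this to days. Assumption: 183 days, with a range of 180 to 184.

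**Formula:** gap = (start day + course length) − 120.

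| Reading | Course ends | Gap | Share of course left |
|---|---|---|---|
| From last dose, 183 days | 0 + 183 = Day 183 | 183 − 120 = 63 days | 63/183 = 34% |
| 72-hour start, 183 days | 3 + 183 = Day 186 | 186 − 120 = 66 days | 66/183 = 36% |
| Shortest: from last dose, 180 days | Day 180 | 60 days | 60/180 = 33% |
| Longest: 72-hour start, 184 days | 3 + 184 = Day 187 | 67 days | 67/184 = 36% |

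Counting true calendar months over every last-dose date in a four-year window gives 61 to 64 days from the last dose and 64 to 67 days with the 72-hour start.

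**Later start.** The course may also begin at discontinuation. Table 5 allows up to 3 weeks after the last infusion for a grade 2–3 non-hematologic toxicity to resolve before the subject is discontinued. If the course began only then, it would end at 21 + 183 = Day 204, a gap of 204 − 120 = 84 days (81 to 85 over the 180 to 184 day range). This is an illustration, not the expected case.

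**Does other text close the gap?**
- Inclusion 9 mentions the course of the study, which could be read to include the 3-year surveillance. But the same sentence ends at 120 days after the last dose, and Section 5.7.2, to which it refers, gives only the 120-day limit.
- The advice in Section 5.7.2 covers trial participation and so plausibly continues through surveillance. It is advice given before enrollment and does not extend the two-method rule.
- Section 7.2.2 covers reporting of pregnancies and Section 7.2.3.1 covers related serious events at any time. Both act after conception. The Section 7.2.2 reporting window can also close 30 days after treatment if new anticancer therapy starts.

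No reading of the current text brings the two end dates together.

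**The case against.** The strongest reply is that the two periods need not match. Contraception is tied to exposure, and the antibiotic course is an extra prophylactic step. Being on prophylaxis does not show that viable vector remains. Phase 1 found no Lm beyond 48 hours without antibiotics, at up to twice this trial's dose, and Day 120 is 60 times that interval. The gap also falls while the woman is taking an antibiotic to which the vector is highly sensitive. The end of the course is not proof that risk ends either, since surveillance runs for 3 years. The visible part of Section 4.2.2 discusses persistence mainly on medical devices, and high-risk devices are excluded.

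Much of this stands. The clearance data make the absolute risk low, and nothing here shows viable Lm at Day 120. Parts of Section 4.2.2, where the Summary of Changes places the delayed-infection case, are not shown. The sponsor may therefore have a reason for 120 days that cannot be seen.

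It does not remove the point. The protocol requires six months of antibiotics despite the 48-hour data, and item 24 of the Summary of Changes gives the reason as the risk of delayed listeria infection. The same revision added the account of an index case (item 6). If that possibility justifies six months of treatment for everyone, it is reasonable for the pregnancy precaution to last as long. The end of the course is a sensible anchor because it is the last active eradication step; the later surveillance only monitors.

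**Conclusion.** The concern holds. Required contraception for women of childbearing potential ends 63 to 66 days before the antibiotic course does, with about 34–36% of the course remaining. The range is 60 to 67 days across standard readings of six months, and longer if the course starts late. This rests on reading Section 5.7.2 as fixing the end at Day 120 and on taking six months as 180 to 184 days.

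It is a misalignment of two safety measures, and no endpoint or analysis is affected. The absolute risk is probably low. The number of women of childbearing potential among the 55 planned subjects is not given, so the number affected cannot be estimated. The change is worth making because the possible harm is severe and the correction is cheap. Confidence is medium, given the text that is not shown.

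**What to change.** In Inclusion 9 and Section 5.7.2, require women of childbearing potential to use two methods of contraception through completion of the 6-month post-treatment antibiotic course, and for at least 6 months after the last ADXS11-001 dose. Tying the end to completion also covers courses that start late. Leave the male requirement (Inclusion 10) at 120 days, because its stated basis is a possible transient effect on sperm. Section 5.7.2 now sets one period for both sexes, so it will need separate wording for women.

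Optionally, in Section 7.2.2, do not apply the 30-day new-therapy cut-off to pregnancies that occur during the antibiotic course.

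The cost is about two more months of contraception for these women (63 to 66 days, more after a late start), plus revised wording in the protocol and consent form. No visit or test is added. Section 5.7.2 bars entry where compliance is in doubt, so the longer commitment slightly tightens eligibility. If the sponsor has a reason to keep 120 days, the protocol should state it.
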